After 72 hrs, the study drug will be discontinued, a primary assessment will be made of primary and secondary endpoints, and all further treatment is at the treating physician's discretion.

Note: Study participants will be permitted to cross over into non-assigned arms of the study, however the study analysis will be completed as an intention-to-treat study. It will be left to the discretion of the primary team, with supervision from the study investigators as to whether a cross over is necessary within the 72 hr study time frame.

Baseline Assessments and Data to be Recorded (all are standard of care unless indicated by *)

1. Directed history and physical exam, focused on signs and symptoms of congestion/volume overload
2. Vital signs (HR, BP, O2 saturation, weight, height)
3. Home medications
4. Basic metabolic panel including serum creatinine, BUN, electrolytes and magnesium
5. Serum Pro-BNP level
6. Serum Cystatin C*
7. High-sensitivity troponin
8. Baseline electrocardiogram
9. Transthoracic echocardiogram if one has not been obtained within 1 year prior to admission
 - i. Including left ventricular (LV) ejection fraction, LV dimensions, left atrium size (LA), LV mass, right ventricular function parameters (RVSP), valvular assessment
10. 6 min walk test*
11. Patient Global Well being assessment by VAS*
12. Dyspnea assessment by VAS*
13. Frailty Index*
14. Blood sample for biomarkers and genetic testing for heart failure*
15. Urine sample for biomarkers*

24 hr Assessment:

1. Routine vitals assessment with weight recording
2. I/O assessment – to be recorded and totaled for each 12 period
3. Twice daily basic metabolic panel and serum magnesium

72 hr Assessment and Data to be Recorded:

1. Routine vitals assessment with weight recording
2. I/O assessment – to be recorded and totaled for each 24 period
3. Twice daily basic metabolic panel and serum magnesium
4. Serum Pro-BNP level*
5. Serum Cystatin C*
6. High-sensitivity troponin
7. 6 min walk test*
8. Patient Global Well being assessment by VAS*
9. Dyspnea assessment by VAS*
10. Frailty Index*
11. Changes in cardiovascular medications
12. Assessment for serious cardiovascular events

At Discharge Assessment and Data to be recorded:

1. Routine vitals assessment with discharge weight recording
2. I/O assessment – to be recorded and totaled for each 24 period
3. Basic metabolic panel including creatinine, BUN
4. Serum Pro-BNP level
5. Serum Cystatin C*
6. High-sensitivity troponin
7. 6 min walk test*

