6. Drugs/ Substances/ Devices

a. The rationale for choosing the drug and dose or for choosing the device to be used.

Furosemide is that standard of care diuretic for patients admitted to the hospital for acute decompensated heart failure. Dopamine at low dose is often used to assist diuresis and reduce acute kidney injury in patients at high risk for acute kidney injury with heart failure from systolic dysfunction.

b. Justification and safety information if FDA approved drugs will be administered for non-FDA approved indications or if doses or routes of administration or participant populations are changed.

N/A.

c. Justification and safety information if non-FDA approved drugs without an IND will be administered.

N/A

7. Study Statistics

a. Primary outcome variables.

1. Percent change in creatinine from randomization to 72 hrs from treatment protocol initiation.

b. Secondary outcome variables.

1. Change in incidence of acute kidney injury (AKI) as defined by Kidney Disease: Improving Global Outcomes (KDIGO criteria summarized below) from randomization to 72 hrs.¹
2. Incidence of AKI as determined by urine output at 72 hrs (KDIGO criteria, summarized below).¹
3. Change in creatinine at 72 hrs adjusted for volume of fluid removal
4. Change in serum cystatin C randomization to 72 hrs
5. Change in NT pro-BNP from randomization to 72 hrs
6. Volume of diuresis measured in liters
 - c) Cumulative volume of diuresis measured in liters
 - d) Cumulative volume of diuresis measured in liters adjusted for BSA
7. Net weight loss at 72 hrs in kg
8. Need for increase in intravenous diuretic dose
9. Change in distance during 6 minute walk test
 - c) From admission to 72 hrs
 - d) From admission to discharge
10. Global well-being assessment score from admission to 72 hrs, and at discharge. To be assessed by a Visual Analog Scale (VAS).
11. Subjective dyspnea score from admission to 72 hrs, and at discharge. To be assessed by a Visual Analog Scale (VAS).
12. Change in frailty index from admission to 72 hrs, and at discharge. To be assessed by the Johns Hopkins Older Americans Independence Center Online Frailty Assessment Tool
13. Length of stay of hospitalization in days

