14. 30 day, 6 month, and 1 year hospital readmission or ER visit for major adverse cardiovascular event, heart failure, renal failure (development of CKD, ESRD, or dialysis need by KDIGO criteria), syncope, or arrhythmia. Readmission events will be adjudicated by a Clinical Event Committee consisting of 2-3 cardiologists not directly in contact with patients enrolled in the study.

KDIGO AKI Definition¹:

AKI is defined by any of the following 3 criteria:

1. Increase in serum creatinine by ≥ 0.3 mg/dl (≥ 26.5 $\mu\text{mol/l}$) within 48 hours; OR
2. Increase in serum creatinine to ≥ 1.5 times baseline, which is known or presumed to have occurred within prior 7 days; OR
3. Urine volume < 0.5 ml/kg/h for 6 hours

Stages of AKI as defined by KDIGO Criteria are as follows:

Stage	Serum Creatinine	Urine Output
1	1.5-1.9 times baseline OR ≥ 0.3 mg/dl (≥ 26.5 $\mu\text{mol/l}$) increase	< 0.5 ml/kg/h for 6-12 hours
2	2.0-2.9 times baseline	< 0.5 ml/kg/h for ≥ 12 hours
3	3.0 times baseline OR increase in serum creatinine to ≥ 4.0 mg/dl (≥ 353.6 $\mu\text{mol/l}$) OR initiation of renal replacement therapy OR, in patients < 18 years, decrease in eGFR to < 35 ml/min per 1.73 m ²	< 0.3 ml/kg/h for ≥ 24 hours OR Anuria for ≥ 12 hours

a. Statistical plan including sample size justification and interim data analysis.

1. Overview:

- a. This is a factorial design study evaluating two simultaneous unrelated interventions. Sample size justification and primary endpoint analysis is described below.

2. Analysis of Primary Endpoints:

- a. The primary analysis will be conducted on an intention-to-treat basis. Non-parametric testing for the continuous primary endpoint (creatinine) will be performed using the Wilcoxon-Mann-Whitney U test. Confirmatory test for interaction between dopamine and diuretic strategy will be performed with linear regression analysis with dopamine*diuretic term, $p=0.10$ for significance.

3. Sample Size Justification:

- a. A difference of 30% in creatinine pre and post- treatment is considered to be clinically meaningful. Setting parameters as follows: two-sided, alpha (Type I error rate) of 0.05, power of 0.80, and using mean creatinine calculations based on our own retrospective experience at

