Johns Hopkins as well as data from prior studies in patients admitted with ADHF, we estimate a sample size of approximately 63 patients per treatment arm. This translates to 63 patients assigned to the diuretic-only treatment arm (intermittent bolus and continuous) and 63 patients assigned to the low-dose dopamine arm (in addition intermittent bolus diuretic and continuous diuretic treatment). Taking into account drop-out rate, we plan to enroll 140 patients (70 per treatment arm; 34 per specific treatment strategy).

4. Randomization:

- a. Patients will be randomized in a blinded fashion to one of four treatment arms upon enrollment. We plan to perform block randomization into the treatment arms and plan to stratify patients by race, CKD status, and receipt of IV contrast dye (during the same admission), as these factors are felt to be significantly associated with the development of AKI.

5. Analysis of Secondary Endpoints:

- a. Summaries of continuous variables will be displayed using the mean, standard deviation, and median. For nominal variables, the number and frequency of subjects in each category will be presented. Statistical tests with p-values < 0.05 will be considered statistically significant, unless otherwise stated.

b. Early stopping rules.

A study subject will be removed from the trial if the above mentioned scenarios from Section 5 were to occur:

- i. The development of hemodynamic instability including hypotension (SBP < 90), hypertensive emergency, or unstable arrhythmias (SVT or VT)
- ii. The development of pulmonary edema requiring inotropes or vasopressor or more than 50% inspired oxygen.
- iii. The development of acute coronary syndrome.
- iv. The development of acute kidney injury as follows:
 - a. If the patient develops Stage II AKI (by KDIGO criteria)¹, the study treatment will be held and a clinical decision will be made whether to resume or discontinue treatment drug
 - b. If the patient develops Stage III AKI (by KDIGO criteria)¹, the study treatment will be discontinued and the patient will be classified as treatment failure and followed only for outcome recording.
 - i. The need for renal replacement therapy
 - ii. New atrial fibrillation or other supraventricular tachyarrhythmia
 - iii. Sustained ventricular arrhythmias

- v. Requirement of furosemide dose increase beyond the study maximum of 200 IV twice daily (or 400 IV over 24 hrs), or the need for addition of thiazide diuretic.

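### The primary Wilcoxon test leaves out the randomisation strata and randomisation creatinine: it is valid, but less powerful than an adjusted rank test if these predict the 72-hour change

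*Combined protocol and SAP*

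**What the plan says.** The primary endpoint (section 2 and section 7, Primary outcome variables) is: "Percent change in creatinine from randomization to 72 hrs from treatment protocol initiation". The primary analysis is by intention to treat, and its test is given in one sentence: "Non-parametric testing for the continuous primary endpoint (creatinine) will be performed using the Wilcoxon-Mann-Whitney U test". No stratification factor or covariate is attached to it.

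Under Randomization, the investigators "plan to stratify patients by race, CKD status, and receipt of IV contrast dye (during the same admission"), and give the reason: "as these factors are felt to be significantly associated with the development of AKI".

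Two other places could have brought these factors in, and neither does. The interaction check is a linear regression that names only the dopamine-by-diuretic term. Secondary endpoint 3 adjusts the creatinine change, but for the volume of fluid removed, which is measured after randomisation.

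On size of effect, the Sample Size Justification says: "A difference of 30% in creatinine pre and post- treatment is considered to be clinically meaningful". No effect estimate or confidence interval is named for the primary endpoint. The nearest text concerns secondary endpoints: "Summaries of continuous variables will be displayed using the mean, standard deviation, and median".

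**The concern.** The plan balances the groups on three factors because it believes they drive kidney injury, then analyses the data as if they had not been recorded. Randomisation creatinine enters only as the denominator of percent change. Dividing by a baseline value does not in general remove its association with the change.

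The two omissions act differently. Stratified blocks remove the strata's contribution to chance differences between groups, but the Wilcoxon null variance still includes it. If the strata predict the outcome, the test therefore runs below its nominal 5% level and loses power. Randomisation creatinine is not a stratification factor, so leaving it out costs power but does not change the level.

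What is at stake is efficiency, not validity: a real effect could be missed more often than necessary in a trial sized for 80% power. A p-value alone also cannot be read against the 30% difference.

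**Working it through.** **Inputs from the documents.** Section 7, Sample Size Justification: two-sided alpha 0.05, power 0.80, a 30% difference, "we estimate a sample size of approximately 63 patients per treatment arm", 140 enrolled. Section 4.a: allocation 1:1:1:1, hence 1:1 on each factor.

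**Not in the documents, so assumed.** The SD, the share of variance explained, the block size (4 used), the stratum prevalences (three binary factors at 50%, 50%, 20%) and the error distribution.

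**The plan's own figure.** With no SD given, 63 cannot be derived from the stated inputs. Solving backwards:

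- d = √(2 × (1.960 + 0.842)² / 63) = 0.499.
- If 30% means 30 points of percent change, SD = 30 / 0.499 = 60 points.
- SDs of 40, 50, 70 and 80 would need 28, 44, 86 and 112 per arm.
- 63 / 70 = 0.90, so the enrolment implies 10% dropout, leaving 126 analysed.

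**Strata and the test's level.** With strata balanced and explaining a share R² of variance, the true level is about 2Φ(−1.96 / √(1 − R²)): 4.4% at 5%, 3.9% at 10%, 2.8% at 20%.

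**Randomisation creatinine.** With equal log-SD at both times and within-patient correlation r (both assumed), it explains (1 − r)² / [2(1 − r)] = (1 − r)/2 of the variance of the log change: 2.5% at r = 0.95, 5% at 0.90, 10% at 0.80. When it alone was predictive, simulated Wilcoxon type I error was 4.4% to 5.4%, about nominal.

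**Power by formula, normal errors, d = 0.5.** Wilcoxon efficiency is 3/π, so the effective n is 63 × 3/π = 60.2 and power = Φ(0.5 × √(60.2/2) − 1.96) = 78.3%. Replacing SD by SD × √(1 − R²) gives, for an adjusted rank analysis, 80.3% (R² 0.05), 82.4% (0.10), 86.6% (0.20) and 90.6% (0.30).

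**Power by simulation.** 6,000 trials per scenario; 140 randomised in stratified blocks, 126 analysed at random; SD 60; shift 30 points. Cells give Wilcoxon vs rank ANCOVA power (%).

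| Variance explained: strata / creatinine | Normal | t, 3 df | Lognormal |
|---|---|---|---|
| 0% / 0% | 77.8 vs 77.6 | 96.8 vs 96.3 | 96.6 vs 96.4 |
| 5% / 5% | 77.0 vs 80.1 | 94.3 vs 96.6 | 94.0 vs 95.6 |
| 10% / 5% | 78.9 vs 83.1 | 94.0 vs 97.0 | 92.5 vs 95.6 |
| 20% / 10% | 78.9 vs 89.4 | 92.1 vs 98.1 | 89.2 vs 96.7 |

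Type I error with normal errors, same row order: Wilcoxon 5.3%, 4.5%, 4.7%, 3.3%; rank ANCOVA 5.2% to 5.5%. Monte Carlo standard error is at most 0.6 points for power and 0.3 to 0.4 for type I error. Smaller repeat runs (3,000 and 4,000 trials) put the normal-error gain at 10%/5% at 4.0 and 5.7 points, against 4.2 here.

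**Each source alone** (3,000 trials, normal errors). Strata 10%, creatinine 0%: 77.4 vs 80.3. Strata 0%, creatinine 10%: 78.4 vs 80.8. Each contributes 2 to 3 points.

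**Ties.** With creatinine rounded to 0.1 mg/dl (assumed median 1.4, log-SD 0.40, r = 0.90; 3,000 trials), power was 77.6% vs 78.5% with strata at 0% and 77.7% vs 81.6% with strata at 10%.

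**Interval.** Mean 95% interval width, normal errors, SD 60: unadjusted 43 points; adjusted 43.7, 41.5, 40.2 and 37.0 in the table's row order. The interval obtained by inverting the rank ANCOVA covered 94.1% to 95.8% over 24 scenarios and disagreed with the test in 0 of 1,500 trials in each.

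**Small-SD case.** If the true effect is 30% and the log-scale SD is 0.30, both tests exceed 99.6% power.

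**The case against.** An unadjusted rank test is a legitimate prespecified choice, and preferring an adjusted one is partly taste. The documents link the strata to AKI, not to percent change in creatinine, and nothing in them links randomisation creatinine to it. The power figures depend on an SD back-solved from one reading of the 30% difference. The plan says it used mean creatinine values, so its planning scale may differ, and with a small SD no power is lost. CKD status and randomisation creatinine overlap, so their variance shares may not add. Race was simulated as binary, although the plan defines no categories. An interval does not require adjustment: a Hodges-Lehmann interval would go with the planned Wilcoxon. Changing the main-effect test while leaving the interaction regression alone would also leave the two inconsistent.

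Much of this stands and sets the size of the point. The gain is conditional and may be small; the degrees-of-freedom cost is untested for a multi-level race factor; the missing interval is a separate gap; and the interaction model should be aligned. None of it removes the main observation. The plan gives its own reason for thinking the strata matter, and its AKI definition rests partly on creatinine rise, so a link is plausible. The cost of adjusting when the covariates are useless is half a point of power or less in these simulations.

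**Conclusion.** The concern holds as an efficiency point. The primary test uses neither the strata nor randomisation creatinine as a covariate. It remains valid: conservative if the strata are predictive, at about its nominal level if only creatinine is.

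At the assumed SD of 60 points and 126 analysed, the power shortfall against rank ANCOVA is nil at 0% of variance explained, about 2 to 4 points at 10-15%, and 6 to 10.5 points at 30%. The last case is the top of the range shown. The variance shares, prevalences, block size and error distributions are all assumptions. The change is worth making because it is nearly free, not because the planned test is wrong.

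**What to change.** Suggested wording for Analysis of Primary Endpoints:

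> The primary test for each factor is a rank ANCOVA. Percent change is ranked over all patients (midranks for ties) and regressed on dopamine, diuretic strategy, race, CKD status and IV contrast as recorded at randomisation, and ranked randomisation creatinine. The effect of each factor is the shift in percent change, in percentage points, at which this test statistic is zero; its 95% CI is the set of shifts that the same test does not reject at two-sided 5%. The unadjusted Wilcoxon test, with its Hodges-Lehmann shift and CI, is a sensitivity analysis. A log-linear geometric mean ratio is supportive only.

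Three details to settle alongside it:

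- Define the race categories.
- Use contrast status at randomisation, since exposure during the same admission could come later.
- State whether the interaction regression carries the same covariates.

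If the effect is not a uniform shift, describe the estimate as a summary of location change.

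A simpler interval is a Hodges-Lehmann shift aligned for the strata, the other factor and randomisation creatinine. Its coverage was 93.7% to 95.2%, and it disagreed with the rank ANCOVA in 1.1% to 3.8% of trials. A linear-model interval beside the rank test is not advised: with heavy-tailed or skewed errors and a true effect, the two disagreed in 7.0% to 16.6% of trials.

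Cost: SAP wording and a short program for the inverted interval. No new data, patients or visits are needed. The strata are known at randomisation, and the baseline list already includes "Basic metabolic panel including serum creatinine, BUN, electrolytes and magnesium". If the covariates explain nothing, power falls by 0.2 to 0.5 points.

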a. Study design, including the sequence and timing of study procedures (distinguish research procedures from those that are part of routine care).

This is a prospective, randomized, non-blinded study. The outcome variable collection will be blinded. Subjects will be randomized (1:1:1:1) within 24 hours of admission for acute decompensated heart failure to one of four treatment groups:

Treatment Protocol:

1. Intermittent bolus (every 12 hrs) furosemide diuretic therapy
2. Continuous infusion furosemide diuretic therapy
3. Intermittent bolus (every 12 hrs) furosemide diuretic therapy plus infusion of low dose intravenous dopamine (3 µg/kg/min)
4. Continuous infusion furosemide diuretic therapy plus infusion of low dose intravenous dopamine (3 µg/kg/min)

Each treatment arm protocol is detailed as follows:

1. Intermittent bolus furosemide diuretic therapy:
 - a. If the patient is not on a prior diuretic dose, a standard dose of furosemide 40mg IV every 12 hrs, with total dose of 80 mg IV over 24 hrs will be initiated.
 - b. If the patient is already on a prescribed diuretic dose, their outpatient dose will be doubled and administered as the equivalent IV dose every 12 hrs. Note: standard furosemide dosing has a 2:1 oral to IV ratio when dosing.
 - i. Example: If the prescribed home dose is furosemide 80mg by mouth twice daily, the inpatient treatment dose will be the IV equivalent of furosemide 160 by mouth twice daily (double the home dose). Therefore, the inpatient treatment dose would be furosemide 80mg IV twice daily).
2. Continuous infusion furosemide diuretic therapy
 - a. If the patient is not on a prior diuretic dose, a standard dose of furosemide 80mg IV over 24 hrs, will be initiated.
 - b. If the patient is already on a prescribed diuretic dose, their outpatient dose will be doubled and administered as the equivalent IV dose, continuously over 24 hrs. Note: standard furosemide dosing has a 2:1 oral to IV ratio when dosing.
 - i. Example: If the prescribed home dose is furosemide 80mg by mouth twice daily (160mg total per day), the inpatient treatment dose will be the IV equivalent of furosemide 320mg total per day. Therefore, the inpatient treatment dose would be furosemide 160mg IV administered continuously over 24 hrs.

3. Intermittent bolus (every 12 hrs) furosemide diuretic therapy plus infusion of low dose intravenous dopamine (3 µg/kg/min)

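### Planned enrolment does not add up: 140 in total and 70 per pooled arm require 35 per strategy, but the plan states 34, which gives 68 and 136.

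*Combined protocol and SAP*

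**What the plan says.** Section 4.a (study design) fixes the allocation: "Subjects will be randomized (1:1:1:1) within 24 hours of admission for acute decompensated heart failure to one of four treatment groups". Section 7, under Randomization, repeats the four-way structure: "Patients will be randomized in a blinded fashion to one of four treatment arms upon enrollment".

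The Sample Size Justification in Section 7 works at a different level. It begins with "we estimate a sample size of approximately 63 patients per treatment arm" and then explains that an arm here is a pooled side of the dopamine comparison. One side is "63 patients assigned to the diuretic-only treatment arm (intermittent bolus and continuous"), the other "63 patients assigned to the low-dose dopamine arm (in addition intermittent bolus diuretic and continuous diuretic treatment"). Each pooled arm is therefore two of the four randomised groups.

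After a general reference to drop-out, with no rate given, the section states the enrolment target: "we plan to enroll 140 patients (70 per treatment arm; 34 per specific treatment strategy"). This is the only place in the document that gives planned enrolment, and the last figure in it is the only patient number given for a single strategy.

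**The concern.** The sentence gives one target at three levels: the whole trial, the pooled arm and the single strategy. With equal allocation each level fixes the other two, so the figures either agree or at least one is wrong. Here the strategy figure does not agree with the other two.

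The practical stake is small but real. Patients are allocated in blocks to the four strategies. Anyone who sets group targets from the only strategy-level number would plan for 136 patients, while anyone who reads the total would plan for 140. Because the drop-out rate is not stated, a reader also cannot tell from the text whether the allowance above the required number is 14 patients or 10.

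**Working it through.** **Inputs**

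| Quantity | Value | Source |
|---|---|---|
| Total enrolment | 140 | Section 7, Sample Size Justification |
| Per pooled arm | 70 | same sentence |
| Per strategy | 34 | same sentence |
| Allocation | 1:1:1:1, four groups | Section 4.a |
| Strategies per pooled arm | 2 | Section 7, Sample Size Justification |
| Required per pooled arm before drop-out | about 63 | Section 7, Sample Size Justification |
| Drop-out rate | not stated | – |

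**Step 1. Total against pooled arm.** 140/2 = 70. These two stated figures agree.

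**Step 2. Strategy size from each.** 140/4 = 35 and 70/2 = 35. Both divisions are exact, so rounding cannot produce 34.

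**Step 3. Reverse check from 34.** 2 × 34 = 68 per pooled arm, not 70. 4 × 34 = 136 in total, not 140. The differences are 1 per strategy, 2 per pooled arm and 140 − 136 = 4 overall, and 4/140 = 2.9%.

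**Step 4. Other readings of the sentence.**
- If an arm meant one of the four groups, 70 per arm would give 4 × 70 = 280, not 140.
- Unequal groups are excluded by the stated allocation ratio.
- If 34 were the number before drop-out, it should be 63/2 = 31.5, and 34 appears after the drop-out adjustment.
- No reserve or replacement pool that could account for four extra patients is described.

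**Step 5. Step from 63 to the enrolment target.** The plan gives no rate, so this is back-calculation only.
- With 70 per arm, the allowance is 70 − 63 = 7 patients, and 1 − 63/70 = 10.0%. In the other direction, 63/0.90 = 70 and 126/0.90 = 140.
- With 68 per arm, the allowance is 68 − 63 = 5 patients, and 1 − 63/68 = 7.4%.
- Margin over the required 2 × 63 = 126: 140 − 126 = 14, against 136 − 126 = 10.

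A round 10% reproduces 70 and 140 exactly. That fits 35 per strategy, but it is an inference.

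**The case against.** The strongest reply is that the discrepancy does not matter. The total and the pooled-arm size are given outright and agree. The trial is sized on the pooled dopamine comparison, and neither the primary analysis nor the interaction test has a sample-size target for a single strategy. The figure 34 therefore drives no other number in the plan. This stands, and it is why the point is minor.

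A second reply is that stratified block randomisation leaves incomplete blocks, so realised groups may differ by a patient or so anyway. That is true of realised numbers, but it does not rescue 34 as a plan: four groups must still average 35 to reach 140.

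A third reply is that the 10% drop-out rate appears nowhere, and that 63 is itself described as approximate, so the neat match with 70 is suggestive and not proof. This also stands. The case does not need it, because the agreement of 140 with 70 is sufficient evidence that 34 is the odd figure out.

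**Conclusion.** The concern holds. Under the stated equal allocation and the plan's own definition of the pooled arms, 140 and 70 require 35 per strategy. The stated 34 is inconsistent with both, by 1 patient per strategy, 2 per pooled arm and 4 in total (2.9%). No reading of the text reconciles the three figures.

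This conclusion uses only stated integers and exact division. The view that 34 is a slip for 35 is a judgement: it rests on the agreement of the other two figures, with weaker support from an inferred 10% drop-out rate.

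Severity is minor. No power shortfall is shown, since both candidate totals exceed 126, and the documents give no standard deviation from which an effect on power could be worked out.

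**What to change.** The sponsor should reconcile the three figures in the Sample Size Justification. The simplest correction is to replace 34 with 35, which leaves 140 and 70 as they are. It costs one digit and touches no design feature, analysis or clinical rule.

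If 34 per strategy was intended, the other two figures should become 68 per pooled arm and 136 in total, which lowers planned enrolment by 4.

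The same edit could usefully state the drop-out rate that was used, so that the step from 63 to the enrolment target can be checked. That is a reporting improvement and not needed to remove the contradiction.
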